## BACKGROUND

According to United Nations statistics, the global population has reached 7.7 billion in 2019, and the population over 65 has reached 700 million, accounting for 9.3% of the world's total population [1]. Taiwan turned into an elderly society in 2018, with 3.31 million people over 65 years old, accounting for 14.1% of the country's total population. It is estimated that it will enter a super-aged society in 2025 [2]. Oral function will gradually degenerate with age; dental diseases, decreased chewing and swallowing functions, and decreased salivary gland function can also affect food intake, cause malnutrition and other problems, and the higher risk of chronic diseases. Elderly people with swallowing dysfunction and poor oral health are 2.6 times more likely to die than those with better oral health [3]. The number of teeth is a crucial factor affecting masticatory function. Several studies have also indicated that older people with fewer posterior teeth and fewer teeth overall are more likely to experience difficulty chewing [4, 5]. Dysphagia and masticatory performance may serve as pathways through which xerostomia affects quality of life [6]. A community-based educational program targeting oral function improvements in older people may be a promising strategy for improving OHRQoL.

Previous studies have highlighted a health disparity between aboriginal and general population[7-9]. The uneven distribution of access to medical resources and insufficient health professional manpower in remote aboriginal villages has led to such health disparities. The aborigines have poor oral hygiene habits and lower level of oral health-related knowledge than those in urban areas [10]. The aborigines living in remote areas have unique cultures, languages, and values. Betel nut is an indispensable item in the traditional society of Taiwan's aborigines. Betel nut chewers usually suffer from severe oral lesions and alveolar bone loss [11,12]. In addition, aboriginal people's dependence on alcohol and smoking rates are also higher than those of ordinary people.

Therefore, the incidence of oral diseases (such as dental caries, periodontal disease, missing teeth, etc.) is higher than that of the general population [13-15]. Lay Health Advisors (LHAs) are chosen from the community; they share similar values, ethnic background, and socioeconomic status, and speak the same language as the people they serve. They are also known as natural helpers and are recommended to provide emotional and social services to local health institutions and communities [16-18]. Its advantages are to save manpower, money and reduce language and cultural barriers. LHA intervention strategies have been widely used in the community-based program, such as cancer screening, smoking cessation, risk behaviors, and the delivery of health information [19-23]. A recent study using an LHA strategy in aboriginal communities in Taiwan has proved more effective than reading leaflets alone for reducing barriers toward oral cancer screening and increasing self-efficacy for oral cancer self-examination [24]. Another study [25] conducting a community-level LHA program that addressed oral health disparities in the access and utilization of dental caries preventive services for immigrant children in Taiwan. A 4-week LHA intervention with one-on-one lessons and experience-sharing proved more effective in improving immigrant children's decay teeth, immigrant mothers' dental caries-related knowledge and maternal preventive behaviors than reading only the brochure.

Employing LHAs strategy can be effective in improving access to care and delivery of health care services for groups that have traditionally lacked access to adequate health care. Oral exercise (i.e., neck exercises, salivary gland massages, and vocal exercises) can effectively improve the oral diadochokinesis (DDK) rate and reduces xerostomia, dysphagia, and poor masticatory performance [9]. Early oral function intervention may be a valuable and actionable target for older adults to maintain quality of life. This is the first study to use the Lay Health Advisor (LHA) strategy to improve the oral function of the older adults in aboriginal communities. In

the present study, we aimed to evaluate the effectiveness of community-based oral exercise with LHA intervention on the oral health-related quality of life, oral function and oral self-care behaviors.

## **METHODS**

### *2.1 Design*

A randomized controlled trial (RCT) was conducted. The participants recruited from aboriginal communities in Eastern Taiwan. Data collecting time was from 2019 to 2020. Participants from the identified communities were randomly assigned to EG or CG using random table.

### *2.2 Participants*

Participants who were 55 years old or above and indigenous people were recruited in the present study. Participants who were disability, have had oral cancer, impaired facial appearance and impaired cognitive function were excluded. Impaired cognitive function was screening by Short Portable Mental Status Questionnaire (SPMSQ). Participants were recruited according to the predetermined minimal sample size estimated based on a type I error = 0.05, power = 0.95, and effect size (ES)  $f = 0.25$  (medium effect in Cohen's  $f$ ) [26]. The number of samples in each group was expected 66 participants. An additional 30% drop out rate was added. The final number of samples for each group were required at least 86 participants. The total sample size was 122 and 118 in EG and CG, respectively.

### *2.3 Instrument*

A structured questionnaire was developed to collect data on demographics (i.e., age, sex, education level), oral function (i.e. swallowing, oral DDK, masticatory performance, saliva flow rate and perceived dysphagia), oral hygiene (i.e. plaque control record, plaque index and Winkel tongue coating index), oral self-care behaviors

(i.e. dental visit, tooth-brushing, and interdental brush) and OHRQoL. Items were reviewed by a panel of experts to assess content validity. The content validity index was 0.89–1.00. To ensure that the study participants understood the content, the questionnaires were pilot tested on 10 indigenous old adults. The reliability of each scale was assessed in terms of internal consistency. Swallowing was assessed with repetitive saliva swallowing test (RSST), masticatory performance was assessed using color-changeable chewing gum (Xylitol, 3.0 g; Lotte, Saitama, Japan) and /pa/, /ta/, and /ka/ syllables was assessed with oral diadochokinesis (DDK) test using KENKOU-KUN (Produced by TAKEI, japan dental supply).

#### *2.4 Outcomes*

##### *2.4.1 Oral health-related quality of life*

OHRQoL was measured using the Geriatric Oral Health Assessment Index (GOHAI), which was translated into Chinese for the participants (GOHAI-T) [27]. For example, “Are you satisfied or happy with the appearance of your teeth, gums or dentures?” Possible responses were range from 1 (always) to 5 (never). The total score ranged from 12 to 60 points. The higher the score, the better the quality of life. Cronbach’s alpha was 0.75 for the scale.

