### *2.6 Intervention*

Oral exercise intervention is designed to increase the range of movement in tongue, lips, and jaw as well as salivary gland massages, which will help speech and/or swallow functioning. All participants performed oral exercise before three meals a day, whereas the participants in the EG also received 4 lessons from a LHA over 4 weeks. Four lessons were taught one-on-one once a week by a certified LHA at the participants' homes. The lessons including understand oral structure, learn oral self-care skills and oral function promotion, understand the status of oral self-care and the relationship between oral diseases and systemic diseases, understand swallowing dysfunction and safe eating skills and review. Teaching tool including oral health leaflets, oral exercise video, dental model, magnets, stickers and oral care logbook. The participants in the CG received leaflets only.

[figure not shown]

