### *2.8 Statistical analysis*

Stata 13.1 (StataCorp LP, College Station, TX, USA) was used for statistical

analysis. A chi-square test and two sample t test were used to compare the demographic variables of the EG and CG. A logistic regression model using generalized estimating equations (GEEs) analyzed the change in oral self-care behaviors between baseline and the follow-ups. Comparisons of OHQoL, oral function index, and dental hygiene index between the EG and CG were analyzed with a linear regression model using GEEs. The effect size (Cohen's  $d$ ) of continuous variables were calculated from the mean difference between baseline and the follow-ups within the EG and CG. An effect of 0.20 is small, 0.50 is medium, and 0.80 is large [26].

The CONSORT flow chart of participant recruitment

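### Section 2.4.1 codes its positively worded GOHAI example item against the stated direction of the total, and no reverse-coding rule is given

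*Combined protocol and SAP*

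**What the plan says.** Section 2.4.1 (Oral health-related quality of life) measures the first-listed outcome with a Chinese translation of the GOHAI. It makes these statements about scoring:

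- One example item: "Are you satisfied or happy with the appearance of your teeth, gums or dentures".
- One response coding, immediately after that example: "Possible responses were range from 1 (always) to 5 (never".
- The range: "The total score ranged from 12 to 60 points".
- The direction: "The higher the score, the better the quality of life".
- The reliability: "alpha was 0.75 for the scale".

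No other section gives a GOHAI scoring rule. Section 2.3 (Instrument) says only that "The reliability of each scale was assessed in terms of internal consistency". Section 2.8 (Statistical analysis) takes the score as given: "Comparisons of OHQoL, oral function index, and dental hygiene index between the EG and CG were analyzed with a linear regression model using GEEs". It also plans a within-arm Cohen's d from baseline to the follow-ups for continuous variables.

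**The concern.** The example item is positively worded: frequent satisfaction is the good state. The only coding in the text gives the lowest value to the most frequent response. That coding suits items asking about problems, where never is the good answer. For the satisfaction item it gives the good answer the low score, while the total is said to rise with better quality of life. As written, the coding, the example and the direction cannot all hold without a recoding step, and none is stated.

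The total enters the EG-CG GEE comparison and the within-arm effect sizes. A reader cannot tell from the text which version of it was analysed, and someone following the text literally would score at least this item backwards. An unreversed item subtracts its improvement from the total instead of adding it, which distorts a between-arm difference in points whenever that item differs between arms.

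**Working it through.** **Inputs from section 2.4.1:** item scores 1 to 5; total 12 to 60; higher is better; alpha 0.75. **Not given:** the number *k* of positively worded items that might be unreversed, and how strongly those items respond to the intervention.

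**1. Reproduce the stated range.** Number of items = 12/1 = 60/5 = 12. The range is 12 × 1 = 12 to 12 × 5 = 60, which agrees with the plan. Reversing an item (6 minus response) maps 1–5 onto 5–1, so the arithmetic limits are the same with or without reversal. The range cannot show which was done.

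**2. Apply the written coding to the example item.**

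| Response | Score as written | Score after 6 minus response |
|---|---|---|
| Always satisfied | 1 | 5 |
| Never satisfied | 5 | 1 |

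Only the right-hand column agrees with the stated direction.

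**3. Effect on the total.** With *k* items unreversed and the others correctly keyed, the best state scores 5(12 − k) + k = 60 − 4k and the worst scores (12 − k) + 5k = 12 + 4k. For k = 1 these are 56 and 16.

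**4. Effect on the EG-CG difference in points.** Let the unreversed items respond *m* times as much as the others. The observed difference divided by the true difference is

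((12 − k) − k·m) / ((12 − k) + k·m).

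For k = 1:

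- m = 1 (all items respond equally): 10/12 = 83%.
- m = 0 (no arm difference on this item): 11/11 = 100%.
- m = 1.5: 9.5/12.5 = 76%.
- m = −0.5: 11.5/10.5 = 110%.

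Nothing in the documents fixes *m*, so 83% is a conditional illustration and not a bound. The ratio applies to points. A standardised effect would change by a different amount, because the SD of the total changes too.

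**5. Whether alpha settles it.** With unit item variances, alpha = (12/11)(1 − 12/V), where V is the variance of the total. Alpha = 0.75 requires V = 12/(1 − 0.75 × 11/12) = 38.4.

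- If all correctly keyed items share one correlation r, V = 12 + r((12 − 2k)² − 12). Correct keying needs r = 26.4/132 = 0.20; one unreversed item needs r = 26.4/88 = 0.30. Both are feasible.
- If positive and negative items are uncorrelated, with a common r within each group, V = 12 + r(k(k − 1) + (12 − k)(11 − k)). Then k = 2 needs r = 26.4/92 = 0.29 and k = 3 needs r = 26.4/78 = 0.34. In this structure, reversing the positive items leaves alpha unchanged.

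The reported alpha is therefore compatible with correct keying and with one or more unreversed items. The text also does not say whether it was computed before or after any recoding.

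**The case against.** The strongest reply is that this is a reporting omission. The plan names an existing instrument, cites a source and states the direction of the total, so the natural reading is that items were keyed to that direction. The anchors may be only the generic response labels, and the example is an English rendering of a questionnaire given in Chinese. Much of this stands: nothing in the documents shows that any item was mis-scored. It does not remove the fault in the text, because the plan states its own coding next to its own example, and the two contradict the stated direction.

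Three stronger readings are tempting but unsupported:

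- *That the GOHAI results are attenuated.* A reader might infer this from the literal coding, but the scoring actually used is not shown, and the size depends on *k* and *m*, neither of which is given.
- *That alpha of 0.75 rules out several unreversed items.* Under equal correlations, three such items would need r = 26.4/24 = 1.10, which is impossible. That result belongs to the equal-correlation assumption; if positive and negative items are uncorrelated, r = 0.34 is enough.
- *That the satisfaction item would not differ between arms because the exercise targets movement and salivary massage.* Section 2.6 has all participants doing the exercise, so it cannot explain the presence or absence of an EG-CG difference. The arms differ in the advisor-led lessons, which include oral self-care skills.

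**Conclusion.** Wrong as written, and minor. The coding in section 2.4.1, applied to its own example, contradicts the stated direction of the total, and no other section corrects it. That conclusion rests on the text alone and needs no model.

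The consequence for results is conditional. The 56 and 16 totals assume that the satisfaction item is the only one unreversed; the 83% figure assumes in addition that all 12 items respond equally. Whether any loss occurred is unknown: recoding may have been done and not reported, or the anchors or the example may be the mistake.

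**What to change.** In section 2.4.1, state that positively worded items, listed individually and including the satisfaction item, are reverse-coded as 6 minus the response before summing. If the anchors or the example are the mistake, correct those instead.

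Then confirm that the analysed totals and the alpha of 0.75 used that rule. The direct check is the recoding step in the analysis file. A quick supporting check is that the satisfaction item, as analysed, correlates positively with the other items, in particular the negatively worded ones. Use only the sign: a clearly negative correlation points to an unreversed item, and a value near zero leaves the question to the recoding step.

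Rerun the GEE comparison, Cohen's d and alpha only if the rule was not used. The cost is one sentence and an item list, one correlation, and a recode line if needed. No new data are required.

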##### *2.4.2 Oral function index*

The Repetitive Saliva-Swallowing Test (RSST) was used to evaluate swallowing. Participants were asked to swallow saliva as many times as possible in 30 seconds [28]. For oral DDK, the participants were asked to repeat the /pa/, /ta/, and /ka/ syllables as quickly as possible, and the number of articulations was counted [29]. Using a digital counter, we separately counted the number of articulations of the /pa/, /ta/, and /ka/ syllables within 10 seconds. Masticatory performance was evaluated using the color-changeable chewing gum (Xylitol, 3.0 g Lotte, Saitama, Japan). This chewing gum contains xylitol, citric acid, and red, yellow, and blue dyes that change color when

subjected to masticatory forces from chewing. The red dye is pH sensitive and changes color under neutral or alkaline conditions. Citric acid maintains a low internal pH of the yellowish-green gum before chewing commences. The gum changes to red when chewed because the yellow and blue dyes seep into saliva, and citric acid elution produces the red color [30]. Participants were asked to chew for 2 minutes. Two minutes later, the observer checked the color of the gum by using a color chart of five color gradations ranging from 1 (very poor) to 5 (very good). Saliva flow rate was measured the saliva flow rate in one minute (ml/min). Participants were asked to chew the gauze for two minutes and spited out the gauze and saliva back into the test tube. After centrifuging the saliva of the gauze, pour the saliva into a measuring tube to measure the volume of the saliva. Perceived dysphagia, which was defined as a subjective perception of problems swallowing, was measured using the swallowing screening scale developed by Ohkuma [31] and has an internal consistency Cronbachα's alpha coefficient of 0.85. Examples of questions included “Do you ever have difficulty swallowing?” “Do you ever have difficulty as a result of cough up phlegm during or after a meal?” “Does it take you longer to eat a meal than it used to?” “Do you feel that it is becoming difficult to eat solid foods?” and “Do you ever have difficulty sleeping because of coughing during the night?” Possible responses were “obviously” (frequently), “slightly” (sometimes), or “no” (never). Respondents with at least one severe symptom were classified as having dysphagia.

#### *2.4.3 Oral hygiene index*

Plaque control record (PCR) was measured the percentage of tooth surface with plaque. PCR range from 0 to 100% [32]. Plaque index (PI) was measured the six indicator teeth 12, 16, 24, 32, 36, 44 and the score for each tooth is range from 0 to 3 (0 = no plaque, 1 = a film of plaque adhering to the free gingival margin and adjacent area of the tooth, 2 = moderate accumulation of soft deposit s within the gingival pocket,

or the tooth and gingival margin which can be seen with the naked eye, 3 = abundance of soft matter within the gingival pocket and/or on the tooth and gingival margin). Then summing the average of 6 indicators teeth. Winkel tongue coating index (WTCI) [33] was measured the accumulation of coating on the surface of the tongue. The tongue was divided into six areas (three posterior and three anterior), and the coating was scored as 0 = *no coating*, 1 = *light coating*, or 2 = *severe coating*; scores ranged from 0 to 12 points.

#### *2.4.4 Oral self-care behaviors*

The question of dental visit, “Do you see a dentist every six months?” Possible responses were “Yes”, “No”. The question of tooth-brushing, “How many times do you brush your teeth a day?” Possible responses were “None”, “One time”, “Two times” and “More than 3 times”. The question of interdental brush, “Do you use an interdental brush every day?” Possible responses were “Yes”, “No” and “Never heard”. The question of flossing, “Do you use dental floss every day?” Possible responses were “Yes”, “No” and “Never heard”.

#### *2.4.5 Covariates*

This study examined age, gender and educational level as covariates.

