#### *2.5 LHA recruitment and training*

A total of 30 people was recruited for LHA training. LHAs are recommended by public health center and tribal community building coordinator as a priority. Selection of LHAs were over 25 years old, indigenous people from the same community, communicated in indigenous language and had a driver license of motorcycle or car. Subsequently, all LHAs received 4-week 15-hour curriculums of training. The training manual was developed to educate the LHAs about association of common oral diseases and systemic diseases in older people, oral care for the older people, teaching principles and methods, working log and practice and final is communication skill. After 4 weeks

of training, 28 trainee LHAs passed the qualification exam and became certified LHAs.

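### The linear model comparing the arms states no role for the baseline value of the outcome; adjusting for it would usually narrow the interval at no data cost (a precision gain, not a bias correction)

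*Combined protocol and SAP*

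**What the plan says.** Section 2.4.5 is the only statement on covariates: "This study examined age, gender and educational level as covariates". It does not say which models they enter, or that the list is complete.

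Section 2.8 describes the between-arm analysis of the continuous outcomes in one sentence: "Comparisons of OHQoL, oral function index, and dental hygiene index between the EG and CG were analyzed with a linear regression model using GEEs". It gives no mean model, visit term, group-by-visit term or working correlation, and it does not mention baseline.

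Baseline is nevertheless collected, and section 2.8 uses it in two other places:
- The logistic GEE "analyzed the change in oral self-care behaviors between baseline and the follow-ups". This concerns the self-care behaviours, not the continuous outcomes.
- The effect sizes (Cohen's d) "of continuous variables were calculated from the mean difference between baseline and the follow-ups within the EG and CG". These are descriptions within each arm, not the between-arm estimate.

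Participants were randomised (section 2.1). Section 2.2 gives the numbers: "The total sample size was 122 and 118 in EG and CG, respectively". The number of follow-ups is not stated.

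**The concern.** When an outcome is measured before and after randomisation, its baseline value is usually the strongest available predictor of the follow-up value. A between-arm model that leaves it out, or that uses it only by subtraction, generally gives a wider interval than the same data allow.

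The linear-GEE sentence leaves two usual readings: follow-up values only, or baseline as one of the repeated responses with a group-by-time (change) contrast. If either is what was fitted, the EG minus CG interval for outcomes such as the GOHAI score is wider than it need be. What is at stake is interval width and a fully stated model, not the validity of the comparison.

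**Working it through.** **The plan's own figure.** Section 2.2 inflates 66 per group by 30%: 66 × 1.30 = 85.8, hence 86. The 66 is reproduced by a repeated-measures between-groups F test with f = 0.25, alpha 0.05 and power 0.95 if one assumes 4 measurements and correlation 0.5. The noncentrality is 0.25² × 132 × 4 / (1 + 3 × 0.5) = 13.2, and power is 0.9501. Neither assumption is in the documents, and the stated inputs contain no term for baseline adjustment. The sample size therefore does not settle which contrast was intended.

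**Inputs.**
- n = 122 and 118 (section 2.2).
- f = 0.25 (section 2.2), which is d = 2 × 0.25 = 0.5 for two groups.
- Baseline to follow-up correlation ρ: not in the documents; taken as 0.3, 0.5 and 0.7.
- Further assumptions: one follow-up, equal variances at baseline and follow-up, independent participants, all 240 analysed, and no variance explained by age, gender or education.

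**Variance of the EG minus CG difference**, in units of σ²(1/122 + 1/118):
- follow-up-only: 1
- change: 2(1 − ρ)
- baseline-adjusted: 1 − ρ²

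The adjusted factor relative to follow-up-only is 1 − ρ². Relative to change it is (1 + ρ)/2. Both are below 1 for 0 < ρ < 1.

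**Half-width** = t(0.975) × √factor × √(1/122 + 1/118), with √(1/122 + 1/118) = 0.1291 and t = 1.970. For example, adjusted at ρ = 0.5: 1.970 × √0.75 × 0.1291 = 0.220.

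| | ρ = 0.3 | ρ = 0.5 | ρ = 0.7 |
|---|---|---|---|
| Half-width (SD), follow-up-only | 0.254 | 0.254 | 0.254 |
| Half-width (SD), change | 0.301 | 0.254 | 0.197 |
| Half-width (SD), adjusted | 0.243 | 0.220 | 0.182 |
| N to match adjusted 240, follow-up-only: 240/(1 − ρ²) | 264 | 320 | 471 |
| N to match adjusted 240, change: 480/(1 + ρ) | 369 | 320 | 282 |
| Power at d = 0.5, follow-up-only | 0.971 | 0.971 | 0.971 |
| Power at d = 0.5, change | 0.903 | 0.971 | 0.999 |
| Power at d = 0.5, adjusted | 0.981 | 0.994 | 1.000 |

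The interval narrows by 5%/13%/29% against follow-up-only and by 19%/13%/8% against change.

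**Limits of the gain.** Estimating the slope costs about 1/(240 − 4) = 0.4% of variance, so there is no gain over follow-up-only below ρ ≈ √(1/236) = 0.065. As ρ approaches 1, (1 + ρ)/2 approaches 1 and the gain over change becomes negligible.

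**Simulation check.** GEE with exchangeable correlation and robust standard errors, three follow-ups, 100 runs per ρ. At ρ = 0.5 the mean standard errors were 0.129 (follow-up-only), 0.129 (change) and 0.112 (adjusted). Across the three correlations the mean estimates lay between 0.275 and 0.310 around a true 0.30. The simulation error at ρ = 0.5 is about 0.129/√100 = 0.013. This is consistent with no bias in any of the three.

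**Why baseline by visit is needed with more than one follow-up.** Take baseline correlations of 0.8 and 0.2 at two visits (assumed, to show a steep decay). A common slope of (0.8 + 0.2)/2 = 0.5 gives factors 1 + 0.5² − 2 × 0.5 × 0.8 = 0.45 and 1 + 0.5² − 2 × 0.5 × 0.2 = 1.05. Visit-specific slopes give 1 − 0.8² = 0.36 and 1 − 0.2² = 0.96. Change gives 0.40 and 1.60. The common slope loses to change at the first visit and to follow-up-only at the second; visit-specific slopes lose to neither.

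**The case against.** The strongest reply is that section 2.8 is silent rather than wrong. On the change reading, baseline is a repeated response and does have a role. A model that includes baseline as a response and constrains the arms to a common baseline mean would already capture essentially the whole gain in the one-follow-up, equal-variance case. This stands as a limit on wording: the plan states no role for baseline, and one cannot say that it excludes baseline. It does not remove the point, because nothing in the text describes the constrained model, and adjustment improves on both usual readings over the correlations examined.

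A reader might infer from the change wording in section 2.8 that the linear analysis is a change analysis. The documents do not support that. The wording sits in the logistic sentence, and the Cohen's d sentence describes each arm separately.

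The size of the gain is also open to challenge. It depends on an undocumented correlation, and 320 is specific to ρ = 0.5, where the two unadjusted contrasts happen to coincide. If age, gender and education explain outcome variance, the further gain depends on a partial correlation that is not given. Section 2.2 allows for 30% dropout. With 85 and 83 analysed, every half-width grows by about √(240/168) = 1.20, although the ratios between methods hardly move. All of this stands, and is why the result is given as a range under stated assumptions.

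Finally, choosing adjustment over a valid unadjusted contrast is a matter of efficiency. That is fair, and it sets the severity.

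**Conclusion.** The point holds as a free improvement in precision: optional, low severity. The plan states no role for the baseline outcome in the linear between-arm model. For assumed correlations of 0.3 to 0.7, adjusting for it would narrow the 95% interval by 5% to 29% against follow-up-only and by 19% to 8% against change. These figures assume one follow-up, equal variances, independent participants, full retention of 122 and 118, and no variance explained by the named covariates.

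Two stronger conclusions are tempting and are not supported:
- That the planned comparison is biased. Allocation was randomised, so both unadjusted contrasts are unbiased.
- That the trial is too small because an unadjusted analysis would need more participants. The equivalent sample sizes only express relative precision. The enrolled numbers exceed the required 86 per group, and with full retention power at d = 0.5 is at least 0.90 under every contrast and correlation examined.

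**What to change.** For the outcomes analysed with the linear GEE, fit the post-baseline values with group, visit, group by visit, the baseline value of the same outcome, baseline by visit (if there is more than one follow-up), age, gender and education. Use robust standard errors. Report the adjusted EG minus CG difference with its 95% interval at each follow-up. State the working correlation, how missing baseline values are handled, and whether the five-grade chewing score is treated as continuous.

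The change does not extend to the logistic behaviour models or to the yes/no dysphagia outcome ("Respondents with at least one severe symptom were classified as having dysphagia"). It also does not deal with clustering by lay health advisor. Section 2.5 reports that "28 trainee LHAs passed the qualification exam and became certified LHAs" and section 2.6 that "Four lessons were taught one-on-one once a week by a certified LHA", so clustering in the EG is a separate matter that needs its own handling.

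The cost is SAP wording and a refit of the linear models; no new data are needed. Data collection ran from 2019 to 2020 (section 2.1), so if the change is adopted after the data were seen, label the analysis post hoc.
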